#### 15.4 Imaging Submission Requirements (REQUIRED\*)

**\* If PET-CT is contraindicated for Patient, sites are to submit the contrast-enhanced CT, MRI or MR-PET from the same timepoint**

PET-CT images must be locally read and interpreted by the local site radiology service. PET-CT must then be submitted to the Imaging and Radiation Oncology Core (IROC) at Ohio (via TRIAD strongly preferred). TRIAD will manage routing these studies to IROC Ohio for Imaging Submission procedures for central data collection, and quality control (QC) check and retrospective review as well as to IROC Rhode Island for the pre-treatment RT QA review as well as central review.

a. Image Collection and Submission Time Points:

Digital image collection is required at the following time points:

1. PET-CT scans must be performed within 42 days prior to registration, as indicated in [Section 5.1c](#) and must be submitted to IROC within 15 days after registration, as indicated in [Section 14.4a](#).
2. Interim PET-CT scans that are performed for clinical purposes after Cycle 2, Day 15 and prior to Cycle 3 must be submitted to IROC within 15 days after the assessment, as indicated in [Section 14.4f](#).
3. End of Treatment PET-CT scans must be performed 4-8 weeks after the last dose of study drug and must be submitted to IROC within 15 days after the assessment, as indicated in [Sections 14.4f, 14.4i, and 14.4l](#).
4. Progression/Relapse PET-CT scans must be performed and submitted to IROC within 15 days after progression/relapse, as indicated in [Section 14.4l](#).

5. 1 year after registration contrast-enhanced CT scans of chest, abdomen and pelvis (+ neck or other involved areas, if involvement at baseline) (or if contra-indicated, PET-CT, CT, MRI, or MR-PET) must be performed and submitted to IROC within 30 days after the assessment, as indicated in [Section 14.4f](#).
6. 2 years after registration contrast-enhanced CT scans of chest, abdomen and pelvis (+ neck or other involved areas, if involvement at baseline) (or if contra-indicated, PET-CT, CT, MRI, or MR-PET) must be performed and submitted to IROC within 30 days after the assessment, as indicated in [Section 14.4f](#).

See also [Section 7.1b](#) for extended allowable windows in event of COVID-19 extenuating circumstance.

b. Digital Image and Radiation Therapy Submission

1. Image Submission Requirements

Submission of treatment plans as DICOM RT is required. Digital data must include treatment planning CT, structures, plan, and dose files.

TRIAD is the American College of Radiology's (ACR) image exchange application. TRIAD provides sites participating in clinical trials a secure method to transmit DICOM RT and other objects. TRIAD anonymizes and validates the images as they are transferred.

TRIAD is the preferred means of image transfer to the IROC. Due to the critical time constraints for submitting data for pre-treatment review, we encourage sites to submit data via TRIAD to ensure that the pre-treatment reviews are completed in a timely manner.

In the event that a site has not completed all steps required for TRIAD data submission in time to meet the timeline for review, data submitted via SFTP will also be accepted. See the instructions for submission of data via SFTP on the IROC Rhode Island website under Digital Data ([www.irocqi.qarc.org](http://www.irocqi.qarc.org)).

2. TRIAD Access Requirements:

TRIAD is the preferred means of image transfer to the IROC. TRIAD should be installed prior to study participant enrollment to ensure prompt secure, electronic submission of imaging and radiation therapy data.

- Site staff who submit images through TRIAD will need to be registered with the Cancer Therapy Evaluation Program (CTEP) and have a valid and active CTEP-IAM account (see [Section 13.2](#)), and be registered as an AP, NPIVR or IVR. Please refer to the CTEP Registration Procedures section for instructions on how to request a CTEP-IAM account and complete registration in RCR.
- To submit images, the site user must be on the site's affiliate rosters and be assigned the 'TRIAD site user' role on the CTSU roster. Users should contact the site's CTSU Administrator or Data Administrator to request assignment of the TRIAD site user role. RAs are able to submit standard of care imaging through the same method.

3. TRIAD Installations:

After a user receives a CTEP-IAM account with the proper user role, he/she will need to have the TRIAD application installed on his/her workstation to be able to submit images. TRIAD installation documentation can be found by following this link <https://triadinstall.acr.org/triadclient/>.

This process can be done in parallel to obtaining your CTEP-IAM account username and password.

If you have any questions regarding this information, please send an e-mail to the TRIAD Support mailbox at [[contact]](mailto:[contact]).

15.5 Patient-Reported Outcomes: Instructions for Administration (**REQUIRED\***)

**\*if patient speaks language in which the assessment tool is available (English, Spanish or French for most tools)**

Patients are required to complete PRO forms at baseline and follow-up timepoints. Questionnaires should be completed at the time of the patient's scheduled clinic visit but if this is not possible then the patient should complete them within  $\pm$  7 days of the follow-up contact. Please see [Section 15.5c.4](#) for methods of administration in cases where patient visit is not conducted in the participating site's clinic.

a. QOL Instruments

The current CIRB-approved PRO (QOL) patient-facing forms are accessible on the CTSU website ([www.ctsu.org](http://www.ctsu.org)) under "Documents" / "CIRB Documents" tab / "Amendment Reviews" subtab.

Patients who are <18 years of age at time of registration and turn age 18 while on protocol will continue to complete the Pediatric QOL assessments for the remainder of the protocol-specified timepoints.

1. Pediatric PROMIS Global (Pediatric) or PROMIS-Global (Adults) (estimated time of completion: 1-2 minutes)

- Available in English, Spanish, and French

2. Pediatric PROMIS Fatigue 10a (Pediatrics);  
PROMIS Fatigue 7a (Adults)  
(estimated time of completion: 2-3 minutes)

- Fatigue 10a: Available in English, Spanish
- Fatigue 7a: Available in English, Spanish, and French.

3. FACT-GOG-NTX (both Pediatric and Adult, modified to remove platinum-related items)  
(estimated time of completion: < 5 minutes)

- Available in English, Spanish, and French

b. Administration Timepoints for all QOL instruments

1. Baseline (prior to registration)
2. Cycle 3 / Day 1 (prior to beginning treatment on Cycle 3)
3. 4-8 weeks after the last dose of protocol therapy (following last dose of study drug or radiation therapy, whichever is later)
4. 1 year after date of registration

5. 3 years after date of registration

**If a patient is removed from protocol therapy prior to an indicated administration timepoint, the indicated assessment tool must still be administered at that timepoint regardless of whether the patient has started a subsequent anti-cancer therapy (after stopping protocol treatment).**

c. Administration of Questionnaires

1. The first time the patient completes the questionnaires: Please read to the patient the instructions attached to each section. Explain the specific administration times for this protocol. Patients should be directed to report all symptoms and limitations whether or not they are related to the cancer or its treatment.
2. It is permissible to assist patients with completing the questionnaires, being careful not to influence the patient's response. Note what assistance was required and indicate the reason in the Comments section (e.g., elderly, too sick, etc.). Discourage family members from: 1) being present while the patient completes the questionnaire and/or 2) influencing patient responses to the questions.
3. If a patient refuses or cannot complete the questionnaire for some reason, then this must be documented in the **S1826** Cover Sheet for Patient-Reported Outcomes.
4. If a patient misses an appointment or is too sick to complete the questionnaires on the scheduled date, a copy of the QOL questionnaires must be provided to the patient (e.g. via e-mail, mail, or sent home with him/her). A telephone (or videoconference) interview must be scheduled and completed within one week of the originally scheduled timepoint. Patient responses to questionnaire items are to be obtained during the telephone (or videoconference) interview while the patient is looking at a copy of the questionnaire. The date of the telephone (or videoconference) interview is to be noted in the Cover Sheet for Patient-Reported Outcomes.
5. If a patient is deemed clinically ineligible after registration but protocol treatment was initiated, he/she should continue the PRO assessments as scheduled. PRO (QOL) assessments continue per scheduled timepoints even if the patient discontinues protocol treatment early and starts a subsequent anti-cancer therapy (after stopping protocol treatment).

d. Administration Quality Control Procedures

When a patient is registered to **S1826**, a calendar should be made with dates of upcoming patient-completed questionnaires noted. A copy of this calendar can be given to the patient with the notation that the questionnaires should be completed before receiving treatment. You may wish to photocopy the Study Calendar, [Section 9.0](#), and include the patient's name and specific dates. A copy of this (if created) should be kept in the patient file.

1. If a patient goes off protocol treatment, continue to administer the patient completed questionnaires according to the protocol-defined assessment schedule (time from registration date).
2. If a patient refuses or cannot complete the patient questionnaires at one time point, he/she should be asked to do so at the next scheduled administration time.
3. The Quality of Life Coordinator will monitor compliance on a regular basis, having been provided with timely reports from the SWOG Statistical Center. The Expectation Report and the MediData RAVE system provides reminders of upcoming quality of life assessments for a patient.

4. Anyone involved in the collection of quality of life data in SWOG trials should review the Patient-Reported Outcome Questionnaires training program available on the SWOG website (under the CRA workbench). The training program is a narrated set of slides designed to standardize the way quality of life data is collected from patients. Questions regarding the quality of life assessments can be addressed to the SWOG Statistics and Data Management Center ([name]).
  
- 15.6 Patient-Reported Outcome Common Toxicity Criteria for Adverse Events (PRO-CTCAE) (**REQUIRED** for English- and Spanish- and French-speaking adult patients and English-speaking pediatric patients)

PRO-CTCAE questions must be administered to English- and Spanish-, and French-speaking patients weekly during the treatment period, as outlined below.

a. Administration Timing

Patients will complete the PRO-CTCAE questions at the following time points:

1. Cycle 1 / Day 1 (prior to beginning treatment)
2. Day 1 of each subsequent treatment cycle (Cycle 2-6) (+/- 7 days)
3. After last dose of study drug (+/- 7 days) and, where applicable, after last dose of radiation therapy, as applicable to the patient) (+/- 7 days)
4. 3-6 months after date of registration (if patient goes off-treatment early) (+/- 7 days)
5. 9, 12, 18, 24, 30 and 36 months after date of registration (+/- 7 days)

**The administration timing of the PRO-CTCAE questionnaire should coincide with the physician-directed toxicity assessment for the respective visit.**

**If a patient is removed from protocol therapy prior to an indicated administration timepoint, the scheduled PRO-CTCAE assessments must continue to be administered until such time that the patient starts a subsequent non-protocol systemic anti-cancer therapy.**

b. Administration Instrument

The current CIRB-approved PRO (PRO-CTCAE) patient-facing forms are accessible on the CTSU website ([www.ctsu.org](http://www.ctsu.org)) under "Documents" / "CIRB Documents" tab / "Amendment Reviews" subtab.

For adult patients ( $\geq$  18 years of age), a total of 19 questions per timepoint will be answered using the Patient-Reported Outcomes Common Terminology Criteria for Adverse Events (PRO-CTCAE). The estimated time of completion for the Adult PRO questionnaire is 10 minutes.

For pediatric patients (12-17 years of age), a total of 33 questions per timepoint will be answered using the Pediatric Patient-Reported Outcomes Common Terminology Criteria for Adverse Events (Pediatric PRO-CTCAE). The estimated time of completion for the Pediatric PRO questionnaire is 15 minutes. Patients who turn age 18 while on protocol will continue to complete the Pediatric PRO-CTCAE assessment for the remainder of the protocol-specified timepoints.

The study-specific PRO-CTCAE items for this protocol can be found in [Section 18.10.](#)

c. Questionnaire Administration Instructions

1. The first time the patient completes the questionnaire: Please read the instructions attached to the patient questionnaire to the patient. Explain the specific administration times for this protocol. Patients should be directed to report all symptoms and limitations, whether or not they are related to the cancer or its treatment.
2. It is permissible to assist patients with completing the questionnaires being careful not to influence the patient's response. Discourage family members from: 1) being present while the patient completes the questionnaire and/or 2) influencing patient responses to the questions.
3. It is very important to review the PRO-CTCAE questionnaire after the patient has completed it to be sure all questions have been answered and that only one answer is marked per question. If the patient has marked more than one answer per question, ask the patient which answer reflects how he/she is feeling. If the patient has skipped a question, tell the patient that a question was not answered and ask if she would like to answer the question. Always give the patient the option to refuse. If the patient declines to answer any question, indicate on the form by the question that the patient did not want to answer this question.
4. If a patient misses an appointment and the physician-directed toxicity assessment is not conducted, then the PRO-CTCAE assessment for that timepoint should be documented as missed on the respective **S1826** PRO-CTCAE form.
5. If the patient appointment is conducted via a telehealth visit within one week of the originally scheduled timepoint, and the toxicity assessment is also conducted via the telehealth visit, then, the PRO-CTCAE questionnaire may also be administered via telephone (or videoconference) at the same timepoint. A copy of the PRO-CTCAE questionnaire must be provided to the patient (e.g. via e-mail or mail), and a telephone (or videoconference) interview may be completed at the same telehealth visit as the toxicity assessment or may be scheduled separately as close to possible (and within the 7-day window of the original assessment timepoint) to the physician-directed toxicity assessment. Patient responses to questionnaire items are to be obtained during the telephone (videoconference) interview while the patient is looking at a copy of the questionnaire.
6. If a patient is deemed clinically ineligible after registration but protocol treatment was initiated, he/she should continue the PRO assessments as scheduled. If the patient discontinues protocol treatment early, the PRO-CTCAE assessments continue at the scheduled timepoints until such time that the patient begins new/different systemic anti-cancer therapy off-protocol.

d. Additional Quality Control Procedures:

When an English-, Spanish-, or French-speaking patient is registered on **S1826**, a calendar should be made with dates of upcoming patient-completed questionnaires noted. A copy of this calendar can be given to the patient with the notation that the questionnaires should be completed.

If a patient refuses or cannot complete the PRO questionnaire at any time **point, he or she should be asked complete the next set of patient questionnaires at the next scheduled assessment time.**

Anyone involved in the collection of quality of life data in SWOG trials should review the Patient-Reported Outcome Questionnaires training program available on the SWOG website (under the CRA workbench). The training program is a narrated set of slides designed to standardize the way quality of life data is collected from patients. Questions regarding the quality of life assessments can be addressed to the SWOG Statistics and Data Management Center ([name]).

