7.7 Patient-Reported Outcomes

a. Quality of Life Assessments

Patients who can complete Patient-Reported Outcome instruments in English, Spanish, or French must complete the baseline PROMIS Fatigue questionnaire, FACT/GOG-Ntx, and the PROMIS Global. The PROMIS Fatigue questionnaire, FACT/GOG-Ntx, PROMIS Global questionnaires will also be administered to these patients at Day 56 (corresponding to the beginning of cycle 3), 4-8 weeks after the last dose of protocol therapy (following last dose of study drug or radiation therapy, whichever is later), and at years 1 and 3 after randomization. The scheduled follow-up PRO assessments should be completed even if the patient goes off protocol treatment early for any reason (including progression). The **S1826** PRO Cover Sheet for Patient Questionnaires is required to be submitted at each PRO assessment time. See [Section 15.5](#) for PRO (QOL) administration procedures. PRO assessments at baseline and follow-up should be completed even if a patient is later deemed clinically ineligible after enrollment. If a patient is removed from protocol therapy prior to an indicated administration timepoint, the indicated assessment tools should still be administered at that timepoint. It will take approximately 15 minutes for the patient to complete the questionnaires at each time point.

b. PRO-CTCAE Assessments

Adult patients who can complete PRO-CTCAE instrument in English, Spanish, or French and Pediatric patients who can complete the PRO-CTCAE instrument in English must complete the PRO-CTCAE questions at the beginning of treatment and weekly during radiation treatment, corresponding to the following time points indicated in [Section 15.6a](#). The administration timing of the PRO-CTCAE questionnaire should coincide with the physician-directed toxicity assessment for the respective visit. If a patient is removed from protocol therapy prior to an indicated administration timepoint, the scheduled PRO-CTCAE assessments must continue to be administered until such time that the patient starts a subsequent non-protocol systemic anti-cancer therapy. See [Section 15.6](#) for PRO-CTCAE questionnaire administration procedures.

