e. WITHIN 15 DAYS AFTER EACH PRO-CTCAE ASSESSMENT INCLUDING CYCLE 1 / DAY 1 (PRIOR TO BEGINNING OF TREATMENT), BEGINNING OF EACH SUBSEQUENT TREATMENT CYCLE (CYCLE 2 - 6), AFTER LAST DOSE OF STUDY DRUG, AFTER LAST DOSE OF RADIATION THERAPY (where applicable), 3-6 MONTHS AFTER DATE OF REGISTRATION (IF PATIENTS GOES OFF-TREATMENT EARLY), 9, 12, 18, 24, 30 AND 36 MONTHS AFTER DATE OF REGISTRATION.

Submit the following:

- **S1826** PRO-CTCAE (Adults) or **S1826** Pediatric PRO-CTCAE (Pediatrics)

f. WITHIN 15 DAYS AFTER EACH DISEASE ASSESSMENT INCLUDING: CYCLE 2 PET-CT (if done for clinical indication), CYCLE 6 (or at the End of Treatment if prior to Cycle 6), AT THE END OF RT (if patients received protocol-specified residual PET RT), and AT 1 YEAR AND 2 YEARS AFTER REGISTRATION

*For after Cycle 2, after Cycle 6 (or at the end of treatment if prior to Cycle 6), and at the end of RT PET-CT*

Submit the following:

- Vital Status Form
- Follow-up Tumor Assessment Form
- Radiology reports from PET-CT, contrast-enhanced CT, MRI, or MR-PET performed to assess disease at each time point. (NOTE: Upload reports via the Source Documentation: Disease Assessment form in Rave®.)
- **S1826** Imaging Adjunctive Data Sheet for PET scans; If PET scan is contraindicated and CT or MRI is submitted, the **S1826** Imaging Adjunctive Data Sheet is not required.  
This form is submitted electronically via the IROC website at: [https://wrightcenterofinnov.qualtrics.com/fe/form/SV\\_cC0Pi8vSYcCnfU](https://wrightcenterofinnov.qualtrics.com/fe/form/SV_cC0Pi8vSYcCnfU). See [Section 14.4a](#) for navigation instructions.
- All PET-CT images (or if PET-CT contraindicated, then all contrast-enhanced CT, MRI or MR-PET) from scans performed to assess disease as specified in [Section 15.4](#). Submit to IROC Ohio (via TRIAD strongly preferred) for retrospective central imaging review.

*For at 1-year and 2-year after registration contrast-enhanced CT*

Submit the following within **30 days** of the above-specified timepoints:

- Follow-up Tumor Assessment Form
- Radiology reports from CT performed to assess disease at each time point. (NOTE: Upload reports via the Source Documentation: Disease Assessment form in Rave®).

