18.10 PRO-CTCAE Common Terminology Criteria for Adverse Events (PRO-CTCAE) Instrument

a. General Information:

The PRO-CTCAE instruments will be used to assess Patient-Reported toxicity outcomes.

Clinician graded CTCAE is the adverse event safety standard. PRO-CTCAE is intended to enhance the quality of adverse event data reporting in clinical trials, provide data that complements and extends the information provided by clinician reporting using CTCAE, represent the patient perspective of the experience of symptomatic adverse events, and improve detection of potentially serious adverse events.

The selection of PRO-CTCAE should be complementary to the clinician identified AEs for ongoing monitoring.

Adverse Event Characteristics: PRO-CTCAE is not intended for expedited reporting, real time review, or safety reporting.

Routine Adverse Event Reporting: Symptomatic Adverse Events reported by patients through PRO-CTCAE are not safety reporting and may be presented with other routine AE data.

PRO-CTCAE (adult and pediatric) assessment tools are available in the following languages. Estimated time of completion: 10 minutes.

- PRO-CTCAE: Available in English, Spanish, and French
- Ped PRO-CTCAE: Available in English

PRO-CTCAE is not currently available on the Medidata Patient Cloud ePRO. Forms are accessible from the [S1826](#) protocol abstract page on the CTSU website at [www.ctsu.org](http://www.ctsu.org). Administration instructions are included in [Section 15.6](#).

Please refer to the [PRO-CTCAE Terms of Use](#) for more information.

b. Recall Period for the PRO-CTCAE measures is: 7 days

c. PRO-CTCAE Analyses

The examination of PRO-CTCAE is exploratory, given there are currently no standardized scoring rules for how to combine attributes into a single score or how best to analyze PRO-CTCAE data longitudinally. PRO-CTCAE responses are scored from 0 to 4. For each of the PRO-CTCAE adverse events examined, the scores for each attribute (frequency, severity and/or interference) will be presented descriptively using summary statistics at each assessment time. Additionally, the worst severity and/or interference over the entire course will be summarized.

d. Study-Specific PRO-CTCAE Questions for Adults ( $\geq 18$  years of age):

Solicited Adverse Events: The following adverse events are considered expected and their presence/ absence should be solicited and severity graded at timepoints indicated in [Section 9.0](#).

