**Attribute Acronyms:**

F: Frequency, S: Severity, I: Interference, P: Presence/Absence/Amount

Symptom AE	Attributes	PRO-CTCAE Items	Response options
Mucositis oral	Frequency	--	--
	Severity	In the last 7 days, what was the SEVERITY of your MOUTH OR THROAT SORES at their WORST?	None, Mild, Moderate, Severe, Very Severe
	Interference	In the last 7 days, how much did MOUTH OR THROAT SORES INTERFERE with your usual or daily activities?	Not at all, A little bit, Somewhat, Quite a bit, Very much
Nausea	Frequency	In the last 7 days, how OFTEN did you have NAUSEA?	Never, Rarely, Occasionally, Frequently, Almost constantly
	Severity	In the last 7 days, what was the SEVERITY of your NAUSEA at its WORST?	None, Mild, Moderate, Severe, Very Severe

Symptom AE	Attributes	PRO-CTCAE Items	Response options
	Interference	--	--
Diarrhea	Frequency	In the last 7 days, how OFTEN did you have LOOSE OR WATERY STOOLS (DIARRHEA/DIARRHOEA)?	Never, Rarely, Occasionally, Frequently, Almost constantly
	Severity	--	--
	Interference	--	--
Abdominal pain	Frequency	In the last 7 days, how OFTEN did you have PAIN IN THE ABDOMEN (BELLY AREA)?	Never, Rarely, Occasionally, Frequently, Almost constantly
	Severity	In the last 7 days, what was the SEVERITY of your PAIN IN THE ABDOMEN (BELLY AREA) at its WORST?	None, Mild, Moderate, Severe, Very Severe
	Interference	In the last 7 days, how much did PAIN IN THE ABDOMEN (BELLY AREA) INTERFERE with your usual or daily activities?	Not at all, A little bit, Somewhat, Quite a bit, Very much
Dyspnea	Frequency	--	--
	Severity	In the last 7 days, what was the SEVERITY of your SHORTNESS OF BREATH at its WORST?	None, Mild, Moderate, Severe, Very Severe
	Interference	In the last 7 days, how much did your SHORTNESS OF BREATH INTERFERE with your usual or daily activities?	Not at all, A little bit, Somewhat, Quite a bit, Very much
Cough	Frequency	In the last 7 days, what was the SEVERITY of	Never, Rarely, Occasionally,

Symptom AE	Attributes	PRO-CTCAE Items	Response options
		your COUGH at its WORST?	Frequently, Almost constantly
	Severity	In the last 7 days, how much did COUGH INTERFERE with your usual or daily activities?	None, Mild, Moderate, Severe, Very Severe
	Interference	--	--
Rash	Frequency	In the last 7 days, did you have any RASH?	Yes, No
	Severity	--	--
	Interference	--	--
Pruritis	Frequency	--	--
	Severity	In the last 7 days, what was the SEVERITY of your ITCHY SKIN at its WORST?	None, Mild, Moderate, Severe, Very Severe
	Interference	--	--

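### Two weekly instructions for PRO-CTCAE conflict with the schedule they point to, the worst-score summary does not say which forms count, and the adult question count is wrong

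*Combined protocol and SAP*

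**What the plan says.** **Schedule.** The opening of Section 15.6 says that "PRO-CTCAE questions must be administered to English- and Spanish-, and French-speaking patients weekly during the treatment period, as outlined below". Section 7.7b says that patients "must complete the PRO-CTCAE questions at the beginning of treatment and weekly during radiation treatment", and in the same sentence refers to the timepoints in 15.6a. The 15.6a list contains:

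- Cycle 1 Day 1, before treatment;
- "Day 1 of each subsequent treatment cycle (Cycle 2-6) (+/- 7 days");
- "After last dose of study drug (+/- 7 days) and, where applicable, after last dose of radiation therapy";
- 3-6 months after registration if the patient is off treatment early;
- 9, 12, 18, 24, 30 and 36 months after registration.

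Section 14.4e (data submission) repeats this list, and 7.6a agrees for the period after treatment. Section 15.6a also stops the forms once non-protocol systemic anti-cancer therapy begins.

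**Analysis.** Section 18.10c calls the PRO-CTCAE work exploratory. It plans descriptive statistics at each assessment time and adds that "the worst severity and/or interference over the entire course will be summarized". Objective 1.2e is a between-arm comparison of these symptoms, stratified by age group.

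**Instrument.** For adults, Section 15.6b says that "a total of 19 questions per timepoint will be answered"; for pediatric patients the stated number is 33. Section 18.10d lists the adult items with their attributes and then tabulates the question wording. Cough is listed with severity and interference.

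**The concern.** Both weekly sentences are phrased as requirements. A site that follows either one literally collects many more forms than a site that follows the list. A per-timepoint mean or proportion does not build up with extra forms, but a maximum does: each added form can raise a patient's worst score and none can lower it. Two patients with the same toxicity can therefore receive different worst scores because one filled in more forms. Section 18.10c does not say whether the course means treatment only or all follow-up, whether the pre-treatment Cycle 1 Day 1 form counts, or whether unscheduled and RT forms count. At stake is whether the worst-score summary supporting objective 1.2e can be read. The adult item inconsistencies raise a separate question: which questions adults were actually asked.

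**Working it through.** **1. Form counts.** Inputs: six 28-day cycles (7.1a); RT lasting about 4 weeks (7.5d); the 15.6a list.

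- Weekly on study drug: 6 × 28 / 7 = 24 forms. List: 6 Day 1 forms + 1 after the last dose = 7.
- Weekly during RT: about 4 forms. List: 1, after the last RT dose.
- Patient given RT, treatment period only: 7 + 1 = 8 under the list; about 7 + 4 = 11 with weekly RT forms.

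**2. Variation under 15.6a alone.** RT adds a form. Stopping treatment early adds a 3-6 month form. Starting non-protocol systemic therapy ends the forms. Counts therefore differ between patients at sites that follow the list exactly.

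**3. How much a maximum moves.** The documents give no per-form rate of high scores and no within-patient correlation, so both are assumed here. With independent forms, P(at least one high score in k forms) = 1 − (1 − p)^k. With correlation 0.5, a beta-binomial with a = p and b = 1 − p gives 1 − B(a, b + k)/B(a, b).

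| Assumed p | Assumed correlation | 7 forms | 8 | 11 | 24 |
|---|---|---|---|---|---|
| 5% | 0 | 30.2% | 33.7% | 43.1% | 70.8% |
| 5% | 0.5 | 12.3% | 12.9% | 14.2% | 17.4% |
| 10% | 0 | 52.2% | 57.0% | 68.6% | 92.0% |
| 10% | 0.5 | 23.5% | 24.4% | 26.7% | 32.0% |

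The direction is the same in every row. The size depends almost entirely on the assumptions.

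**4. Between-arm consequence through RT.** Section 11.2 expects RT almost exclusively in pediatric patients, with a slightly higher rate on N-AVD. Section 2.6 anticipates about 15% RT use in childhood patients. Section 2.9 plans 317 + 27 = 344 pediatric patients among 579 + 64 + 317 + 27 = 987. So 0.15 × 344 ≈ 52 patients, and 52 / 987 ≈ 5% of the trial.

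As a deliberately large case, take a 15-point difference in RT use between arms (the first action threshold in 11.2) and weekly RT forms. At equal toxicity the worst-score rate shifts by 0.15 × [P(11) − P(7)]:

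- p = 5%: 0.15 × 12.9 = 1.9 points if independent; 0.15 × 1.9 = 0.3 with correlation 0.5.
- p = 10%: 0.15 × 16.4 = 2.5 points if independent; 0.15 × 3.2 = 0.5 with correlation 0.5.

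**5. Adult question count.** Stated: 19. Counting attribute letters in 18.10d, from mucositis to decreased sexual interest: 2+2+1+1+3+2+2+1+1+2+3+3+3+1 = 27. The two other-symptoms items make 29. The same method on the pediatric list gives 3+3+2+2+3+3+3+1+2+2+3+3+3 = 33, which reproduces the stated 33. The adult figure of 19 appears only if all 8 interference items are dropped (27 − 8 = 19), which contradicts the list.

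**6. Adult wording table.** Vomiting is listed for frequency but has no row. For cough, the severity question sits in the frequency row with frequency answers. The question "In the last 7 days, how much did COUGH INTERFERE with your usual or daily activities" sits in the severity row with severity answers, and the interference row is blank.

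**The case against.** The strongest reply is that the schedule is clear in substance. The 15.6 sentence defers to the list beneath it, 7.7b defers to 15.6a, and every detailed list agrees. Sections 7.7b and 15.6 also tie the form to the physician's toxicity assessment. This stands: the intended schedule can be identified, so the three statements are not irreconcilable. It does not remove the problem that two mandatory sentences say something else.

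The reply on importance also largely stands. Confusion over weekly forms on study drug affects both randomised arms. The worst score is a secondary descriptive summary, in a section that calls itself exploratory and attaches no test or power to it.

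A reader might infer large inflation of the worst score, or a material bias against N-AVD. The documents do not support this. Large figures need an assumed event rate and independence between one patient's forms, and RT is expected in only about 5% of the trial.

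A reader might also infer that a faulty cough item could hide pneumonitis on nivolumab. That does not follow. Section 8.2 bars PRO-CTCAE from driving any protocol-directed action, 8.6 makes clinician-graded CTCAE the safety standard, and 11.5 keeps PRO-CTCAE out of adverse event stopping rules.

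Finally, the vomiting and cough faults are seen in a table read from PDF, and the cough entry is split at a break. The forms patients complete are posted separately (15.6b) and were not available here. The table faults therefore call for a check; they do not show that data were lost.

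**Conclusion.** The point holds at a modest level. Sections 15.6 and 7.7b contain weekly instructions that their own schedule does not contain: 24 against 7 forms on study drug and about 4 against 1 around RT. The worst-over-course summary has no rule on which forms enter it, and form counts vary between patients even when 15.6a is followed. That a maximum cannot fall as forms are added is certain. The size of the effect is unknown, because it rests on a per-form rate and a within-patient correlation that the documents do not give. Any between-arm bias is probably small: 0.3 to 2.5 points across the assumed values shown, even with a 15-point difference in RT use. The per-timepoint summaries do not accumulate with form count, and the primary endpoint is not involved. The adult count of 19 is inconsistent with the 27-item list (29 with other symptoms). The vomiting and cough rows remain to be verified.

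**What to change.** 1. Delete the weekly wording in 15.6 and in 7.7b, so that the list in 15.6a and 14.4e is the only schedule.
2. In 18.10c, define the worst score over a fixed set of scheduled timepoints common to all patients (for instance Day 1 of each cycle plus the form after the last study drug dose). State whether the pre-treatment form counts. Keep extra RT, early-off-treatment and unscheduled forms out of it.
3. Report the number of forms completed by arm beside the worst score, since early stopping still leaves some patients with fewer forms.
4. Correct the adult count in 15.6b to match the 18.10d list.
5. Check the source page and the fielded adult form for the vomiting item and for the cough questions and answer scales. If the faults are confirmed, correct them and describe how the cough responses already collected will be handled.

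The cost is a few text edits and one check of the fielded form. No assessment is added, and forms already collected remain usable in the per-timepoint summaries.
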